4.1.2 Completed Clinical Trial

MK-8504 Protocol 001 was a 2-part, double-blind, randomized, placebo-controlled, single-rising-dose study in healthy male and female (non-childbearing potential) subjects. Overall, single oral doses of MK-8504 up to 120 mg were generally well tolerated in healthy adult males and females. No SAEs, events of clinical interest (ECIs), or deaths were reported. A total of 25 subjects enrolled in the trial. One subject discontinued due to a non-drug related AE of depression after receiving placebo. No trends were observed between AE incidence and increasing dose levels, and there were no AE findings consistent with renal or bone toxicity. No clinically meaningful trends were observed for changes in clinical laboratory values, vital signs (VS), or ECGs as a function of dose or treatment.

Following oral administration, MK-8504 is rapidly absorbed ($T_{max} \sim 0.5h$) and displays a biphasic elimination profile with a $t_{1/2}$ of $\sim 8h$ at high doses. Due to the short $t_{1/2}$, no plasma accumulation is expected. Following oral administration, MK-8504 is taken up into PBMCs, metabolized into TFV and subsequently phosphorylated to form TFV-DP. TFV-DP only leaves the cells in the form of TFV. Plasma TFV therefore has a delayed C_{max} (T_{max} in the range of 1 to 4h) and larger AUC when compared to the PD MK-8504 because it is formed by multiple metabolic processes following MK-8504 administration. Plasma TFV has a $t_{1/2}$ in the range of ~ 29 to 38 h. PBMC TFV-DP has a T_{max} in a range of 12 to 24 h and displays a biphasic elimination profile which is only observed at high doses (likely due to the sensitivity of the analytical method). The calculation of the $t_{1/2}$ considering the last phase provides a $t_{1/2}$ of ~ 96 to 165 h, which supports a QW regimen. Considering the PBMC target C_{168h} , an accumulation ratio of ~ 1.3 to 1.5 is expected for a QW regimen. Food lowered peak and

extent of exposure of plasma MK-8504 and TFV but did not decrease the exposure of PBMC TFV-DP. Therefore MK-8504 may be dosed without regard to food.

Detailed safety and pharmacokinetic data from Protocol 001 can be found in the Investigator Brochure (IB).

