4.2.2.3 Rationale for Dose Interval and Trial Design

MK-8504, a TFV PD, is not considered a compound with higher potential for risk of harm to volunteers according to the publication "Guideline on Strategies to Identify and Mitigate Risks for First-in-Human Clinical Trials with Investigational Medicinal Products" (European Medicine Agency guidance released July 2007) [5]. It is not a biological molecule, does not exhibit highly species-specific action, nor is it directed towards immune system targets. Furthermore, it acts via a well-established mechanism, inhibition of HIV-1 reverse

transcriptase, for which multiple marketed agents act similarly (TDF, lamivudine, emtricitabine, abacavir, didanosine, stavudine, and zidovudine).

The trial design includes up to four sequential panels of six subjects each. If MK-8504 is administered to more than one subject on the same day, it will be dosed in spaced time intervals must have a minimum of five to ten minutes between administering to individual subjects by the Phase I Clinical Research standards for compounds not considered to be of high risk.

There will be a minimum of 35 days between dosing of MK-8504 in consecutive panels to allow for assessment of safety data and potential AEs as well as evaluation of PK and viral dynamic data from previous panels to inform dose selection.

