5.2.1.2 Dose Modification (Escalation/Titration/Other)

All dose escalation decisions will be made jointly by the investigator and the Sponsor. Each dose escalation decision will occur after at least 6 subjects have completed the previous dose level.

Dose escalation decisions will be based on key safety variables including: vital signs, 12-lead ECGs, laboratory safety tests, adverse events and review of viral dynamic data from the previous dose levels up to at least 24 hours (or longer depending on the compound). Pharmacokinetic and pharmacodynamic data must be included in the dose escalation decisions. See Background & Rationale - Section 4.0.

If, as judged by the Sponsor and investigator, the safety and tolerability data do not justify dose escalation, the dose will not be increased as planned. Instead, subjects may:

- receive the same dose level to further explore safety and tolerability at that level;
- receive a lower dose of the trial drug;
- receive the same or lower dose as a divided dose; or
- receive a lower dose with or without food.

Or, dosing may be stopped. Subject discontinuation criteria are outlined in Section 5.8.

Prior to each treatment, the clinical and laboratory safety parameters from the previous dose level will be reviewed by the investigator and discussed with the Sponsor to permit a decision on whether to advance to the next higher dose level. No dose escalation will occur without the joint agreement of the investigator and the Sponsor.

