5.11 Clinical Criteria for Early Trial Termination

There are no pre-specified criteria for terminating the trial early.

A primary objective of this early Phase I trial is to identify the maximum safe and well-tolerated dose and/or dosing regimen that achieve pharmacokinetic, pharmacodynamic and/or biologic targets in humans based on preclinical or early clinical data. Therefore, it is possible that trial subjects may not receive all doses specified in the protocol if this objective is achieved at lesser dose levels in this trial. This would not be defined as early termination of the trial, but rather an earlier than anticipated achievement of the trial objective(s). If a finding (e.g., pharmacokinetic, pharmacodynamic, efficacy, biologic targets, etc.) from another preclinical or clinical trial using the trial treatment(s), comparator(s), drug(s) of the

same class, or methodology(ies) used in this trial, results in the trial(s) or program being stopped for non-safety reasons, this also does not meet the definition of early trial termination.

Early trial termination is defined as a permanent discontinuation of the trial due to unanticipated concerns of safety to the trial subjects arising from clinical or preclinical trials with the trial treatment(s), comparator(s), drug(s) of the same class or methodology(ies) used in this trial.

Enrollment of the trial will be halted in the following circumstances:

1. One subject reports a serious adverse event with a potential causal relationship to the study drug or two (2) subjects per panel report severe adverse events with a potential causal relationship to study drug.
2. Three (3) or more of the enrolled subjects experience the same adverse event requiring withdrawal from the study, or the same severe adverse event assessed as having a potential causal relationship to study drug.
3. Two (2) severe but not life threatening adverse experiences or severe clinically significant laboratory abnormalities that are similar in nature OR one (1) severe and life threatening adverse experience laboratory abnormality OR participant death thought to be potentially related to the investigational product.
4. Two (2) or more of the enrolled subjects experience confirmed QTcF > 500 ms or QTcF change from baseline >60ms in a given panel.

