If the circumstances outlined in (1) or (2) or (3) above occur, enrollment and dosing will be halted and an internal safety review will be conducted, and the Sponsor will notify the competent authority where required of a halt to enrollment. Following the internal safety review, if the Sponsor deems it appropriate to restart enrollment and dosing, if required the Sponsor will submit a notification to the competent authority prior to restart. If approved, enrollment and dosing may restart at that time. If the circumstances outlined in (4) occur, enrollment and dosing will be halted and all available safety data will be reviewed to inform a decision about whether the study should continue. The safety of subjects will be assessed on an ongoing basis, and while conditions that could warrant early trial termination are not limited to those noted above, these criteria are meant to pre-specify circumstances under which the trial may be terminated early.

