7.1.5.2 Treatment Period

7.1.5.2.1 Predose Procedures (All Panels)

Prior to each treatment, the clinical and laboratory safety parameters from the previous dose level and previous treatment panel will be reviewed by the Investigator and the Clinical Team and a mutual decision on whether to advance to the next higher dose level will be made. No dose escalation will occur without agreement of the Investigator and the SPONSOR.

Subjects will report to the CRU the day prior to the scheduled day of administration of the study drug or time specified by the investigator. Subjects will fast from all food and drink, except for water, for a minimum of 8 hours prior to study drug administration and prior to obtaining samples for laboratory safety tests (refer to Section 7.1.3.1).

After the Day 1 predose procedures have been completed, subjects will be assigned a unique randomization number associated with a specific treatment sequence as defined by a

computer-generated allocation schedule. For details on procedures, please refer to the Study Flow Chart (Section 6.0), Procedures (Section 7.1.2) and/or corresponding appendices.

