7.1.5.5 Trial Design/Dosing/Procedures Modifications Permitted within Protocol Parameters

This is a Phase I assessment of MK-8504 in humans, and the pharmacokinetic, pharmacodynamic and safety profiles of the compound is still being elucidated. This protocol is written with some flexibility to accommodate the inherent dynamic nature of Phase I clinical trials. Modifications to the dose, dosing regimen and/or clinical or laboratory procedures currently outlined below may be required to achieve the scientific goals of the trial objectives and/or to ensure appropriate safety monitoring of the trial subjects.

As such, some alterations from the currently outlined dose and/or dosing regimen may be permitted based on newly available data, but the maximum daily dose may not exceed those currently outlined in the protocol.

- Repeat of or decrease in the dose of the trial drug administered
- Interchange of doses between panels
- Entire panel(s) may be omitted
- Instructions to take trial drug with or without food or drink may also be modified based on newly available data
- Modification of the PK/PD sample processing and shipping details based on newly available data
- Decrease in the length of postdose pharmacokinetic/pharmacodynamic sample collection

The pharmacokinetic/pharmacodynamic sampling scheme currently outlined in the protocol may be modified during the trial based on newly available pharmacokinetic or pharmacodynamic data (e.g., to obtain data closer to the time of peak plasma concentrations). If indicated, these collected samples may also be assayed in an exploratory manner for metabolites and/or additional pharmacodynamic markers.

The timing of procedures for assessment of safety procedures (e.g., vital signs, ECG, safety laboratory tests, etc.) currently outlined in the protocol may be modified during the trial based on newly available safety, tolerability, pharmacokinetic or pharmacodynamic data (e.g., to obtain data closer to the time of peak plasma concentrations). Additional laboratory safety tests may be added to blood samples previously drawn to obtain additional safety information (e.g., adding creatinine kinase to serum chemistry panel that was already drawn).

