7.2.4 Evaluating Adverse Events

An investigator who is a qualified physician will evaluate all adverse events with respect to the elements outlined in [Table 6](#). The investigator's assessment of causality is required for each adverse event. Refer to [Table 6](#) for instructions in evaluating adverse events.

Table 6 Evaluating Adverse Events

Maximum Intensity	Mild	awareness of sign or symptom, but easily tolerated (for pediatric trials, awareness of symptom, but easily tolerated)
	Moderate	discomfort enough to cause interference with usual activity (for pediatric trials, definitely acting like something is wrong)
	Severe	incapacitating with inability to work or do usual activity (for pediatric trials, extremely distressed or unable to do usual activities)
Seriousness	A serious adverse event (AE) is any adverse event occurring at any dose or during any use of Sponsor's product that:	
	† Results in death ; or	
	† Is life threatening ; or places the subject, in the view of the investigator, at immediate risk of death from the event as it occurred [Note: This does not include an adverse event that, had it occurred in a more severe form, might have caused death.]; or	
	† Results in a persistent or significant disability/incapacity (substantial disruption of one's ability to conduct normal life functions); or	
	† Results in or prolongs an existing inpatient hospitalization (hospitalization is defined as an inpatient admission, regardless of length of stay, even if the hospitalization is a precautionary measure for continued observation. (Note: Hospitalization for an elective procedure to treat a pre-existing condition that has not worsened is not a serious adverse event. A pre-existing condition is a clinical condition that is diagnosed prior to the use of a Merck product and is documented in the patient's medical history.); or	
	† Is a congenital anomaly/birth defect (in offspring of subject taking the product regardless of time to diagnosis); or	
	Is a cancer (although not serious per ICH definition, is reportable to the Sponsor within 24 hours to meet certain local requirements); or	
	Is associated with an overdose (whether accidental or intentional). Any adverse event associated with an overdose is considered a serious adverse event for collection purposes. An overdose that is not associated with an adverse event is considered a non-serious event of clinical interest and must be reported within 24 hours.	

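### Halting rule 4 counts QTcF cases per panel (at least for the >60 ms limb), so one case in each of two panels at a repeated dose forces no halt; the practical loss is narrow

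*Combined protocol and SAP*

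**What the plan says.** Section 5.11 lists four circumstances that halt the trial. Rule 4 is the only one that names QTcF: "Two (2) or more of the enrolled subjects experience confirmed QTcF > 500 ms or QTcF change from baseline >60ms in a given panel". When it is met, "enrollment and dosing will be halted and all available safety data will be reviewed to inform a decision about whether the study should continue". The competent-authority notification attached to rules 1 to 3 does not apply to rule 4.

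Each panel has 6 subjects (section 2.2, Table 1), and a subject joins only one panel (section 5.3, Table 3). The dose need not rise from panel to panel. If safety and tolerability do not justify escalation, section 5.2.1.2 allows that subjects may "receive the same dose level to further explore safety and tolerability at that level". Section 7.1.5.5 also lists "Repeat of or decrease in the dose of the trial drug administered" among the changes permitted within the protocol, documented by a letter to the Trial File. No section says whether rule 4 cases from an earlier panel at the same dose still count.

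**The concern.** A repeated dose means new subjects, in a new panel, at an exposure already studied, and section 5.2.1.2 offers it to learn more about safety at that dose. Yet the rule 4 count restarts at zero. Two cases among 6 subjects in one panel halt dosing. One case in each of two panels at the same dose, 2 of 12, does not.

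The other rules do not reliably fill this gap. Rule 3 and part of rule 2 count across panels, but for a QTcF finding they need severe events, or three withdrawals for the same event. Table 6 (section 7.2.4) defines severe as "incapacitating with inability to work or do usual activity", which an asymptomatic QTcF change need not meet. Rule 1 needs a related serious event, or two related severe events in a panel. The gap therefore concerns asymptomatic, non-serious prolongation.

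Safety is a primary objective (section 3.1). At stake is a pre-specified, mandatory pause in place of a discretionary one.

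**Working it through.** **Which limb is affected.** The words about a given panel close a sentence with two limbs, >500 ms and a change >60 ms. They can be read as limiting both limbs or only the second. The >60 ms limb is counted per panel on either reading.

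**Inputs.** Panel size n = 6 and threshold of 2 cases come from the protocol. The protocol gives no operating characteristics for rule 4, so there is no stated figure to reproduce. The per-subject rate p of a confirmed case is not given either, so it is an assumption here. Section 4.1.2 reports for healthy subjects at single doses up to 120 mg: "No clinically meaningful trends were observed for changes in clinical laboratory values, vital signs (VS), or ECGs as a function of dose or treatment". That favours low rates at those doses. The present trial may go to 240 mg, and the documents report no ECG results above 120 mg.

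**Formulas**, for two panels of 6 at one dose, with independent subjects:

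- Halt as written: 1 − [P(at most 1 of 6)]².
- Halt if the count is carried over: P(at least 2 of 12).
- Difference, which is exactly one case in each panel: [6p(1−p)⁵]².

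**Worked example at p = 0.02.** P(exactly 1 of 6) = 6 × 0.02 × 0.98⁵ = 0.1085, and 0.1085² = 0.0118.

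| Assumed rate | Halt as written | Halt if carried over | Missed (points) |
|---|---|---|---|
| 1% | 0.3% | 0.6% | 0.3 |
| 2% | 1.1% | 2.3% | 1.2 |
| 5% | 6.4% | 11.8% | 5.4 |

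If exactly 2 of the 12 have a case, the split is one per panel in 6 × 6 = 36 of 66 arrangements (54.5%), and the per-panel count misses all of these. All figures are conditional on a dose being repeated, for which the documents give no probability.

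**Who would have been protected by the pause.** Section 4.2.2.3 says that dosing several subjects on one day "must have a minimum of five to ten minutes between administering to individual subjects". Six subjects have five gaps, so at the minimum spacing dosing is finished after 5 × 5 = 25 to 5 × 10 = 50 minutes. The first postdose ECG is at 1 hour (section 6.0). With same-day dosing at that spacing, no halt based on the repeat panel's own ECGs could spare anyone in that panel, and only replacement subjects (section 5.9) remain. If dosing is spread over days, subjects of the repeat panel not yet dosed are affected too. The protocol does not say which will happen.

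**The case against.** The strongest reply is that the protocol already puts a stop before any later panel. At least 35 days must separate dosing of consecutive panels, expressly for safety review (section 4.2.2.3). The last scheduled ECG is at 600 hours, or day 25 (section 6.0), so a panel's scheduled ECGs normally fall inside that gap. Before each treatment, safety data from "the previous dose level and previous treatment panel will be reviewed by the Investigator and the Clinical Team" (section 7.1.5.2.1). Rule 4 itself ends only in a data review. This largely stands: for a later panel, carrying the count over adds little beyond a formal halt. The review is, however, framed around whether to escalate, and it has no QTcF count that forces a stop.

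Single cases are also managed. Under section 7.1.2, a QTcF rise of at least 60 ms leads to two repeat ECGs and, if confirmed, to monitoring every 15 minutes. The Sponsor should be notified if it persists. A confirmed value above 500 ms leads to Sponsor notification, cardiologist review, and telemetry or consideration of transfer. These steps protect the individual subject but do not halt dosing.

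Finally, 2 of 12 (16.7%) is half the observed incidence of 2 of 6 (33.3%), so pooling with the same threshold is a stricter rule. That is true and lowers the priority. But the consequence is a temporary halt for review, and rules 2 and 3 already use absolute counts not confined to a panel.

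A reader might infer that two QTcF cases at one dose could pass unreviewed, or that serious prolongation escapes every rule. The documents do not support either: the review is compulsory, and a related case that leads to inpatient admission is serious and halts under rule 1 alone.

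**Conclusion.** The gap is real on the text but narrow. If a dose is repeated, one asymptomatic, non-serious confirmed case in each of two same-dose panels forces no halt, certainly for the >60 ms limb. The mandatory pause is lost mainly for subjects of the repeat panel not yet dosed, when dosing is spread over days, and for replacement subjects. A later panel is largely covered by existing provisions.

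Conditional on a repeat, the loss is 0.3 to 1.2 points at assumed rates of 1% to 2%, and 5.4 points at 5%. A reader could be tempted by larger numbers: 12.6 points at a rate of 10%, or the mathematical maximum of 16.2 points at a rate of 1/6. Nothing in the documents supports rates that high, so these should not be taken as the expected size. The planned escalation, with no repeated dose, is unaffected.

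**What to change.** Add one sentence to section 5.11: for rule 4, subjects are counted per panel or cumulatively over all panels given the same dose level, whichever is met first. Keep both QTcF limits and the threshold of two subjects.

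This needs no extra subjects or procedures. The cost is a somewhat higher chance of a temporary halt, at a lower observed incidence, and only when a dose is repeated: 0.6% instead of 0.3% at a 1% rate, 2.3% instead of 1.1% at 2%, and 11.8% instead of 6.4% at 5%. It is a cheap improvement of low priority.

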6.0 TRIAL FLOW CHART

Panels A, B, C and D																			
		Scheduled Time																	
		Hours Postdose																	
	Prestudy	Pre-dose	0	0.25	0.5	1	2	4	6	12	24	36	48	72	96	168	240	384	600/Post-trial ^a
Administrative Procedures																			
Informed Consent	X																		
Informed Consent for Future Biomedical Research ^b	X																		
Inclusion/Exclusion Criteria	X																		
Subject Identification Card	X																		
Medical History	X																		
Assignment of Screening Number	X																		
Assignment of Randomization Number ^c		X																	
Prior/Concomitant Medication Review	X	X	X	X	X	X	X	X	X	X	X	X	X	X	X	X	X	X	X
Clinic Procedures/Assessments																			
Full Physical Examination	X	X ^d														X			X
Height	X																		
Weight	X																		
12-Lead Electrocardiogram ^e	X	X				X					X					X			X
Vital Signs (heart rate, blood pressure) ^f	X	X				X					X					X			X
Orthostatic Vital Signs (heart rate, blood pressure) ^f	X	X				X					X					X			X
Vital Signs (respiratory rate, oral/tympanic temperature)	X	X				X					X					X			X
Standard Meals ^g								X	X	X	X	X	X	X	X	X	X	X	X
MK-8504 Administration			X																
Adverse Events Monitoring	X	X	X	X	X	X	X	X	X	X	X	X	X	X	X	X	X	X	X
Laboratory Procedures/Assessments																			
Laboratory Safety Tests (hematology, chemistry, urinalysis)	X	X ^d									X					X			X
Urine /Serum β -Human Chorionic Gonadotropin (β -hCG) ^h	X	X ^d																	X
Serum FSH ⁱ	X																		
Urine/Blood Drug Screen ^j	X	X																	
HIV/Hepatitis Screen	X																		
Blood for Genetic Analysis ^b		X																	
Pharmacokinetic/Pharmacodynamic Evaluations																			
Blood for Plasma MK-8504 and TFV Assay ^k		X	X	X	X	X	X	X	X	X	X	X	X	X	X	X	X	X	X

Panels A, B, C and D																				
		Scheduled Time																		
		Hours Postdose																		
		Prestudy	Pre-dose	0	0.25	0.5	1	2	4	6	12	24	36	48	72	96	168	240	384	600/Post-trial ^a
Blood for MK-8504 PBMC Assay ^{l, n}			X						X		X	X		X	X	X	X	X	X	X
Blood for HIV RNA, Viral Resistance ^{m, n}		X	X						X		X	X		X	X	X	X	X	X	X
CD-4 cell Count		X																		

- a. The post-trial visit will occur approximately 25 days following administration of the study drug. Follow up for any clinical or laboratory adverse experiences should occur by phone or in person if the post-trial visit occurs prior to 25 days following the last dose of study drug. For confirmation of viral load return to baseline, additional data from viral load samples collected during routine follow-up visits may be transmitted to the sponsor for those patients who do not begin ART and who provide appropriate informed consent.
- b. This sample should be drawn for planned analysis of the association between genetic variants in DNA and drug response. This sample will not be collected at the site if there is either a local law or regulation prohibiting collection, or if the IRB/IEC does not approve the collection of the sample for these purposes. If the sample is collected, leftover extracted DNA will be stored for future biomedical research if the subject signs the FBR consent. If the planned genetic analysis is not approved, but FBR is approved and consent is given, this sample will be collected for the purpose of FBR. This sample, to be collected on randomized subjects only, should be obtained one time only, predose, on Day 1 (or with the next scheduled blood draw) or at a later date.
- c. On Day 1, the randomization number is assigned after the completion of all pre-dose procedures prior to trial drug administration.
- d. The pre-dose PE and laboratory assessments may be performed within 24 hour prior to dosing.
- e. Pre-dose ECG will be performed within 3 hours prior to study drug administration and will consist of 3 repeat measurements with at least 1 minute intervals between ECG measurements. Recording may commence after the subject has remained in a semi-recumbent position for at least 10 minutes. (See Section 7.1.2 for additional details).
- f. Pre-dose semi-recumbent HR and BP will be duplicate measurements obtained at least 1-2 minutes apart within 3 hours prior to study administration. Subjects should be resting in the semi-recumbent position for at least 10 minutes prior to obtaining HR and BP. Following each semi-recumbent HR and BP measurement, subjects assume a standing position for 2 minutes and then orthostatic HR and BP will be obtained. See Section 7.1.2 for additional details.
- g. Standardized meals will be provided at ~4 and ~10 hours post-dose. A snack will be offered at ~7 and 13 hours post-dose. After the 24 hour postdose procedures have been completed, subsequent meal and snacks will be unrestricted in terms of caloric content, composition and timing.
- h. For female subjects of childbearing potential only. Urine pregnancy test may be performed at predose.
- i. For postmenopausal woman only.
- j. Additional urine drug screen tests may be performed at the discretion of the PI.
- k. Leftover main study plasma will be stored for future biomedical research, if the subject consents to Future Biomedical Research consent.
- l. For all panels PBMC samples may be collected up to the post-trial visit regardless of initiation of ART.
- m. For all panels blood for HIV-1 viral RNA and viral resistance may be collected up to the post-trial visit if subjects do not start ART. Blood for HIV-1 viral RNA and viral resistance will only be collected if subjects do not initiate follow-on ART for timepoints >168 hours.
- n. For blood collection at 240, 384 and 600 hour timepoints, a window of +/- 24 hrs is acceptable. The 600 hour sample may be collected at the post-trial visit. Leftover main study PBMC will be stored for future biomedical research if the subject consents to Future Biomedical Research consent.

